1.2. Study Objectives

1.2.1. Primary Objectives

The primary objective of the study is to evaluate the reduction of LDL-C by evinacumab in comparison to placebo after 16 weeks in patients with primary hypercholesterolemia (heterozygous familial hypercholesterolemia [HeFH], or non-HeFH with a history of clinical atherosclerotic cardiovascular disease [ASCVD]) with persistent hypercholesterolemia despite receiving maximally-tolerated LMT. Persistent hypercholesterolemia is defined as LDL-C ≥ 70 mg/dL (1.81 mmol/L) for those patients with clinical ASCVD and LDL-C ≥ 100 mg/dL (2.59 mmol/L) for those patients without clinical ASCVD.

1.2.2. Secondary Objectives

The secondary objectives of the study are:

- To evaluate the dose-response effect of evinacumab on other lipid parameters (ie, Apolipoprotein B [ApoB], non-high-density lipoprotein cholesterol [non-HDL-C], total cholesterol [TC], Lipoprotein(a) [Lp (a)], triglycerides [TGs], ApoCIII), and total ANGPTL3 in patients with primary hypercholesterolemia
- To evaluate the safety and tolerability of subcutaneous (SC) and intravenous (IV) doses of evinacumab in patients with primary hypercholesterolemia
- To assess systemic concentrations of evinacumab in serum in patients with primary hypercholesterolemia
- To evaluate the potential development of anti-evinacumab antibodies

1.2.3. Modifications from the Statistical Section in the Final Protocol

The summary of modifications is listed in the following table.

Item	Protocol Section	Description
1	10.3.1.1 Intent-to-Treat (ITT)	SAP Section 3.1.1 Evaluable primary endpoint requirement for the primary analysis population was removed per FDA request.
2	10.3.2.1 Double-Blind Safety Analysis Set/second item “For patients receiving study drug from more than 1 treatment group during the trial, the treatment group allocation for as-treated analysis will be the one in which the patient was treated with the highest number of injections (Group A) or infusions (Group B).”	SAP Section 3.2: The second item for determining the as-treated treatment group will be conservatively changed to: “For randomized patients receiving both evinacumab and placebo study treatment during the trial, the treatment group allocation for as-treated analysis will be evinacumab.
3	10.4.3.1 Primary Efficacy Analysis “Each model will include the fixed categorical effects of treatment group (placebo and evinacumab dose regimens), randomization strata, time point (weeks 4, 8, 12, 16 for the Group B treatment groups; weeks 2, 4, 6, 8, 12, 16 for the Group A treatment groups)”	SAP Section 5.7.1 Timepoints in the MMRM model are updated: “Each model will include the fixed categorical effects of treatment group (evinacumab dose regimens versus placebo), randomization strata (high-intensity statin [Yes/No] and HeFH status

Item	Protocol Section	Description
		[Yes/No]), time point (weeks 2, 4, 6, 8, 12, 16 for the Group B treatment groups; weeks 2, 4, 6, 8, 10, 12, 14, 16 for the Group A treatment groups)”
4	4.2.2. Secondary Efficacy Analysis 
 • Proportion of patients with calculated LDL-C < 100 mg/dL (2.59 mmol/L) at week 16 • Proportion of patients with calculated LDL-C < 70 mg/dL (1.81 mmol/L) at week 16 	SAP Section 4.7.2 These two secondary endpoints were removed due to the protocol amendment for changes to the inclusion criteria. Specifically, the LDL-C threshold was lowered to aid patient enrollment, potentially allowing patients to achieve one or both of the secondary endpoints at baseline.

1.2.4. Revision History for Statistical Analysis Plan Amendments

The following modification has been made in this SAP version 2, as compared to version 1.

Item	SAP Section	Description
1	Appendix 10.2	The upper bound for Week 16 in Table 1 and 2 (analysis windows for Group B) was increased by 2 days (from study day 126 to 128). These extra 2 days in the week 16 analysis window will reduce the missing data rate for the primary efficacy endpoint.

2. INVESTIGATION PLAN

2.1. Study Design and Randomization

This is a phase 2, randomized, double-blind, placebo-controlled, dose-ranging study to assess varying doses of SC and IV regimens of evinacumab in patients diagnosed with primary hypercholesterolemia (HeFH, or non-HeFH with a history of clinical ASCVD) who have an LDL-C ≥ 70 mg/dL (1.81 mmol/L) for those patients with clinical ASCVD and LDL-C ≥ 100 mg/dL (2.59 mmol/L) for those patients without clinical ASCVD, despite receiving a stable maximally-tolerated LMT. The LMT should include a stable, maximally-tolerated statin and stable PCSK9 inhibitor antibody for patients who are HeFH, or non-HeFH with a history of clinical ASCVD. Patients with HeFH not on a statin are eligible if there is documentation of

inability to tolerate at least 2 statins (see Protocol Section 7.3) Background Treatments for further information).

Patients who meet all inclusion criteria and who meet none of the exclusion criteria will be randomized within either Group A (1:1:1:1) or Group B (1:1:1) to receive:

Group A

- Evinacumab 300 mg SC QW for 16 weeks, or
- Evinacumab 300 mg SC Q2W, for 16 weeks (alternating with placebo on opposite weeks), or
- Evinacumab 450 mg SC QW, for 16 weeks, or
- Placebo SC QW, for 16 weeks

Group B

- Evinacumab 5 mg/kg IV Q4W, for 24 weeks, or
- Evinacumab 15 mg/kg IV Q4W, for 24 weeks, or
- Placebo IV Q4W, for 24 weeks

Enrollment of IV cohorts will occur before enrollment of SC cohorts, accordingly, enrollment of Group A will not begin until Group B enrollment is completed.

Patients enrolled to the SC (Group A) and IV (Group B) treatment groups will have different visit schedules because of the differences in dosing frequency.

Randomization will be stratified by high-intensity statin (Yes/No) and HeFH (Yes/No) at baseline. High-intensity statin is defined as rosuvastatin 20 mg or 40 mg daily, atorvastatin 40 mg or 80 mg daily, or simvastatin 80 mg daily (if already on this dose for >1 year). To ensure an adequate number of patients with HeFH are included in this study and exposed to each dose, randomization will be stratified 2:1 (HeFH:non-HeFH; 24:12) within each treatment group.

2.2. Sample Size and Power Considerations

Four pairwise comparisons of evinacumab to a placebo control arm corresponding to the route of administration (Group A or Group B) are hypothesized for the primary efficacy analysis of this study. A total of 216 patients are planned for assessing the primary measure at week 16. Specifically, a sample size of 36 patients per treatment arm will have 90% power to detect a treatment group difference in mean percent change LDL-C of 20% in any 1 pairwise comparison (ie, evinacumab mean = 27% and control mean = 7%), assuming that the common standard deviation (SD) is 25 using an independent group t-test. This sample size has been adjusted for a 5% dropout rate. The alpha level for each of the 4 pairwise comparisons is 0.05 (2-sided), and assumes control of the overall type-1 error rate using a pre-specified hierarchical inferential approach.

Further, the evinacumab 5 mg/kg IV Q4W regimen has been added to Group B, allowing for an assessment of dose-response in the IV route of administration. The additional 36 patients for this second IV dose regimen culminate in a total of 252 patients planned for the study.

With the intent to gain evinacumab experience across these dose regimens for future study planning in patients with HeFH, a subgroup analysis is planned for the stratified sub-population of patients diagnosed with HeFH. To ensure an adequate number of patients are randomized into the HeFH strata level, a total of 175 patients are planned for assessing the percent change LDL-C from baseline at week 16. Specifically, a sample size of 36 patients per treatment arm will have 90% power to detect a treatment group difference in mean percent change LDL-C of 20% in any 1 pairwise comparison (ie, evinacumab mean = 27% and Control mean = 7%), assuming that the common SD is 20 using an independent group t-test. This sample size has been adjusted for a 5% dropout rate.

Blinded Sample Size Adjustment

Referencing the ICH E9 regulatory guidance, the study sample size may be re-estimated after approximately 75% of the patients reach the week 8 visit in the double-blind period, to ensure adequate power in the case of a larger-than-expected variability in the data. This sample size re-estimation process may be performed twice; once for Group A and again for Group B. The sample size re-estimation will be based on the actual blinded pooled SD (adjusted as described in Keiser 2003) for the primary efficacy measure. Since the patients’ post-baseline LDL-C levels are masked to all study participants (patients, site personnel, and sponsor staff), the blinded pooled SD will be calculated by a designated statistician external to Regeneron who has access to the lipid data. As mentioned in Keiser 2003, the blinded sample size re-estimation does not affect type-I error materially for continuous endpoints.

This re-estimation procedure will assess the need for an increase or decrease in sample size (unrestricted recalculation). The result of this procedure is non-binding, since the decision to increase the sample size will also take into account other study execution factors (for example, availability of patients). In the case the re-estimated sample size is implemented, a protocol amendment will document the modification.

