7.6. Method of Treatment Assignment

Patients will be randomized within either Group A (SC treatment regimens) in a 1:1:1:1 ratio or Group B (IV treatment regimens) in a 1:1:1 ratio. Enrollment of IV cohorts will occur before enrollment of SC cohorts; accordingly, enrollment of Group A will not begin until Group B enrollment is completed. There will be 144 patients randomized to Group A (36 patients per treatment group), with 108 patients exposed to SC evinacumab and 36 exposed to SC placebo. There will be 108 patients randomized to Group B (36 patients per treatment group), with 72 patients exposed to IV evinacumab and 36 exposed to IV placebo.

Patients in Group A will receive treatment from day 1 through week 16 (last dose of study drug at week 15). Patients in Group B will receive treatment from day 1 through week 24 (last dose of study drug week 20). Patients will be randomized to a treatment group according to a central randomization scheme provided by an interactive voice response system (IVRS)/interactive web response system (IWRS) to the designated study pharmacist (or qualified designee).

Randomization will be stratified by study treatment route of administration (Group A or B), high-intensity statin (Yes/No), and HeFH (Yes/No) at baseline. High-intensity statin is defined as rosuvastatin 20 mg or 40 mg daily, atorvastatin 40 mg or 80 mg daily, or simvastatin 80 mg daily (if already on this dose for >1 year). To ensure that an adequate number of patients with HeFH are included, randomization will be stratified 2:1 (HeFH:non-HeFH; 24:12) within each treatment group.

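### The HeFH power statement gives 36 patients per arm; its inputs require 25, and the 24:12 stratification supplies 24

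*SAP*

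**What the plan says.** SAP 2.2 and Protocol 10.2 carry the same two calculations, one after the other.

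- **Whole population.** 36 patients per arm for 90% power to detect a 20-point difference ("ie, evinacumab mean = 27% and control mean = 7"), "assuming that the common standard deviation (SD) is 25 using an independent group t-test". The significance level is given here: "The alpha level for each of the 4 pairwise comparisons is 0.05 (2-sided". On dropout: "This sample size has been adjusted for a 5% dropout rate".
- **HeFH subgroup.** "a total of 175 patients are planned for assessing the percent change LDL-C from baseline at week 16". The next sentence makes this specific: "LDL-C from baseline at week 16. Specifically, a sample size of 36 patients per treatment arm will have 90% power", again for a 20-point difference, but now "assuming that the common SD is 20 using an independent group t-test", and again with 5% dropout. No significance level is given for this calculation.

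The number of HeFH patients is also fixed by the randomisation. Protocol 7.6 says that "randomization will be stratified 2:1 (HeFH:non-HeFH; 24:12) within each treatment group". The same 24:12 split appears in the protocol synopsis, in Protocol 5.1 and 6.2, and in SAP 2.1. Protocol 6.1 sets every one of the seven arms at 36 patients, 252 in all.

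**The concern.** The two calculations share the difference, the power and the dropout rate, and differ only in the SD (25 against 20). The required sample size grows with the square of the SD, so the two cannot both end at 36 per arm.

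The HeFH figure also conflicts with the rest of the plan without any power calculation. Seven arms of 36 HeFH patients make 252, the whole trial, which leaves no room for the non-HeFH patients that the stratification reserves.

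The subgroup calculation is there to support planning of later HeFH studies. Someone who takes it at face value would credit the HeFH comparison with 36 patients per arm when the design gives it two-thirds of that, and would find two different HeFH totals, 175 and 168.

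**Working it through.** **Inputs.** Difference 20 points; SD 25 (whole population) and SD 20 (HeFH); power 90%; dropout 5%; two independent groups of equal size, t-test (all SAP 2.2). Two-sided 0.05 is stated for the primary comparisons and is assumed for HeFH. Seven arms: four in Group A and three in Group B (SAP 2.1).

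**Method.** With n evaluable patients per arm, the t-test has 2n − 2 degrees of freedom and non-centrality (difference/SD) × √(n/2). Power comes from the non-central t distribution. Randomised per arm = evaluable/(1 − 0.05), rounded up.

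**Step 1. Reproduce the main calculation (SD 25).** Standardised difference = 20/25 = 0.8. The solution is n = 33.8, so 34; at 34 the non-centrality is 0.8 × √17 = 3.30 and power is 90.15%. Then 34/0.95 = 35.8, so 36 randomised. The plan's 36 reproduces, so the method matches the one behind the plan.

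**Step 2. Repeat for HeFH (SD 20).** Standardised difference = 20/20 = 1.0. The solution is n = 22.02. At 22, power is 89.97%; at 23, the non-centrality is √11.5 = 3.39 and power is 91.25%. So 23 evaluable, and 23/0.95 = 24.2, so 25 randomised. Over seven arms, 7 × 25 = 175, exactly the stated HeFH total.

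**Step 3. Compare the three HeFH sizes at SD 20.**

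| HeFH per arm | Source | Seven arms | Power, all evaluable | Power after 5% dropout |
|---|---|---|---|---|
| 36 | HeFH sentence | 252 | 98.7% | 98.3% (34.2 evaluable) |
| 25 | implied by 175/7 | 175 | 93.4% | 92.1% (23.75 evaluable) |
| 24 | 24:12 stratification | 168 | 92.4% | 91.0% (22.8 evaluable) |

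The HeFH sentence exceeds the requirement by 36 − 25 = 11 patients per arm (44%) and the design's supply by 36 − 24 = 12 (50%). The stratification falls short of the stated total by 175 − 168 = 7 patients, one per arm.

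**Step 4. Look for another route to 36 at SD 20 and 90% power.** One-sided 0.05 gives 19 randomised. Two-sided levels of 0.025, 0.0125 and 0.01 give 29, 33 and 34. Inflating for dropout by multiplication instead of division does not change these results. The normal approximation at two-sided 0.05 gives 22 evaluable and 24 randomised. None gives 36; at two-sided 0.05, 36 corresponds to about 98% power.

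**Step 5. Sensitivity to the SD.** If the HeFH SD were 25, as assumed for the whole population, 24 per arm with 5% dropout would give 75% power, against about 90% with 36 per arm.

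**The case against.** The strongest reply is that the sentence refers to arms of 36 and does not say 36 HeFH patients. Every arm does have 36 patients, of whom 24 are HeFH, and those 24 give 91% power after dropout, close to the stated 90%. On that reading the sentence is only badly worded. It does not hold up: the sentence spells out the HeFH total that comes just before it, uses the HeFH SD, and applies the dropout adjustment to the number it gives. Even if the reading is accepted, 175 still disagrees with 168.

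Several other points stand and limit the weight of the finding.

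- The HeFH p-values are descriptive (Protocol 10.4.3.4, SAP 5.7.1.3) and outside the testing hierarchy, so primary inference is untouched.
- The gap between 24 and 25 per arm is small, and the normal approximation gives exactly 24.
- The 24:12 split is a planned allocation; the documents do not call it an enrolment limit.
- The figure of 25 is never printed, and two-sided 0.05 is an assumption for this calculation.
- Nothing in the documents says that the HeFH SD is 25, and the planned analysis is a repeated-measures model in the full ITT population. The 75% is therefore a conditional illustration and not the power of that analysis.

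**Conclusion.** The concern holds. The HeFH paragraph states a sample size that does not follow from its own inputs and that the design does not provide. The correct requirement is 23 evaluable or 25 randomised per arm, consistent with the printed total of 175; the allocation supplies 24 per arm, 168 in total. The 36 was most likely carried over from the SD 25 sentence, but that is an inference.

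The consequence is a wrong statement about the subgroup, not a loss of power at the planned SD: 24 per arm gives about 91% after 5% dropout, or just under 90% if evaluable patients are rounded down to 22. This rests on SD 20, a 20-point difference, two-sided 0.05 and a plain two-group t-test. The correction should be made because the plan states a size and power for this analysis and stratifies the randomisation to secure its numbers.

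**What to change.** In the HeFH paragraph of both Protocol 10.2 and SAP 2.2:

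- replace 36 per arm with 24 HeFH patients per arm (168 in total);
- give the power as about 91% for a 20-point difference at SD 20 after 5% dropout, and state the significance level used (two-sided 0.05);
- delete 175;
- optionally add that power would be about 75% if the HeFH SD were 25.

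If the sponsor prefers to keep 175 as the requirement, the sentence should read 25 per arm, and the 24:12 split must then be reconciled with it wherever it appears. The first option follows the allocation already in place. It is a text correction in two documents, with no extra patients and no change to the analysis.

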2.3. Study Plan

The study consists of 4 (for Group A [SC treatment groups]) or 5 (for Group B [IV treatment groups]) periods: a run-in period (for patients whose background LMT has not been stable prior to screening, who are not already receiving a PCSK9 inhibitor antibody, or whose background LMT is not optimized), a 2-week screening period, a 16-week double-blind treatment period for the SC dose groups or 24-week double-blind treatment period for the IV dose groups, an approximately 48-week open-label treatment period for the IV dose groups, and a follow-up period lasting 24 weeks after the last dose of study drug (Figure 1).

The Study event table is presented in Appendix 10.7 .

Figure 1: Study Flow Diagram

	Run-in	Screening	Double-Blind Treatment	Open-Label Treatment	Follow-Up Period
			Group A: SC x 16 weeks Group B: IV x 24 weeks	Group B: IV x 48 weeks	Group A: 23 weeks Group B: 20 weeks
Variable	(Day -14)	Baseline (Day 1)	End of Double-Blind (Day 113/ Day 169)	End of Open-Label (Approx Day 505)	End of Study (Day 274/ Day 645)

3. ANALYSIS POPULATIONS

In accordance with guidance from the International Conference of Harmonization of Technical Requirements for Registration of Pharmaceuticals for Human Use (ICH) guideline ICH E9 Statistical Principles for Clinical Trials (ICH, 1998), below are the patient populations defined for statistical analysis. Two efficacy populations are planned for this study, specifically the Intent-to-Treat (ITT) population and the Modified Intent-to-Treat population (mITT). The primary efficacy analysis population is the ITT population. Additional patient populations are defined for safety, anti-drug (evinacumab) anti-body (ADA), pharmacokinetic (PK), pharmacodynamic (PD), and open-label analyses. For the purposes of the definitions below, a patient is considered randomized to study treatment when they have been screened and received a double-blind treatment kit number allocated and recorded in the IVRS/IWRS database, regardless of whether the treatment kit was used or not.

As with all trials, odd cases (usually rare) occur for patient eligibility in the analysis populations. The following are three cases with the planned resolution of each type of case should they occur.

- Patients administered study treatment without randomization or before randomization will not be considered as “randomized” and therefore will not be included in any analysis population. The safety experience from these patients will be reported separately.
- For patients found to be randomized and treated more than once in this trial, safety data from the first randomization and treatment will be included in the safety population, with safety data associated with the later randomization and treatment reported separately. Inclusion of efficacy data from the patient randomized and treated more than once in the two efficacy populations will be decided on a case-by-case basis prior to the unblinding of treatment assignments and documented in the study report.
- Patients successfully randomized and administered study treatment, but later found to violate inclusion/exclusion criteria, will be included in all analyses with appropriate documentation for the protocol deviation.

3.1. Efficacy Analysis Sets

3.1.1. Intent-to-Treat (ITT)

The ITT population (also known as the full analysis set) is defined as all randomized patients who received at least 1 dose or part of a dose of double-blind study drug. Patients in the ITT population will be analyzed according to the treatment group allocated by randomization (ie, as-randomized group).

3.1.2. Modified Intent-to-Treat (mITT)

The modified ITT (mITT) population is defined as the all randomized population who took at least 1 dose or part of a dose of study drug and have an evaluable primary endpoint. The endpoint is considered evaluable when both of the following conditions are met:

- Availability of at least 1 measurement value for calculated LDL-C before first dose of study drug (i.e., baseline).
- Availability of at least 1 calculated LDL-C value during the efficacy treatment period and within one of the efficacy analysis windows in the DBTP up to week 16. The group A (SC dose regimens) efficacy treatment period is defined as the time from the first study drug administration up to 14 days after the last double-blind study drug injection. The Group B (IV dose regimens) efficacy treatment period is defined as the time from the first study drug administration up to 35 days after the last double-blind study drug infusion, or up to the first dose of the open-label study drug, whichever is earlier.

Patients in the mITT population will be analyzed according to the treatment group allocated by randomization.

3.2. Double-Blind Safety Analysis Set

The double-blind safety analysis set (SAF) considered for safety analyses will be the randomized population who received at least 1 dose or part of a dose of double-blind study drug. Patients will be analyzed according to the treatment received (placebo IV, evinacumab 5 mg/kg or 15 mg/kg IV Q4W, placebo SC, evinacumab 300 mg SC QW or Q2W, evinacumab 450 mg SC QW). Actual treatment received is defined as follows:

- For Group A, each study drug administration visit is assigned 3 kits with 150 mg IP concentration in each kit, and each kit contains either evinacumab or placebo. Different combinations of evinacumab or placebo kits determine the actual dosage as follows:
 - For the evinacumab 450 mg SC QW treatment group, the 3 kits at all weekly visits contain evinacumab as recorded in eCRF “Study Drug Administration- Evinacumab/Placebo SC”
 - For the 300 evinacumab mg SC QW treatment group, 2 kits contain evinacumab and 1 kit contains placebo at all weekly visits as recorded in eCRF “Study Drug Administration- Evinacumab/Placebo SC”
 - For the 300 evinacumab mg SC Q2W treatment group, 2 kits contain evinacumab and 1 kit contains placebo at all even-numbered weekly visits (Day 1, Week 2, Week 4, etc.) as recorded in eCRF “Study Drug Administration- Evinacumab/Placebo SC.” All odd-numbered weekly visits (Week 1, Week 3, etc.) contain 3 kits of placebo as recorded in eCRF “Study Drug Administration- Evinacumab/Placebo SC”
 - For the placebo SC QW treatment group, the 3 kits at all weekly visits contain placebo as recorded in eCRF “Study Drug Administration- Evinacumab/Placebo SC”
- For Group B, each study drug administration visit is assigned 1 kit, and it contains either evinacumab or placebo (regardless of evinacumab dose). The actual study

treatment received (placebo, evinacumab 5mg/kg IV, or evinacumab 15 mg/kg IV) is defined as follows:

- Active study treatment (evinacumab or placebo) is defined from the kit number in eCRF “Study Drug Administration- IV”
- Evinacumab study treatment dose (5 mg/kg or 15 mg/kg) is defined as “active study treatment = evinacumab” and the dose is defined in the “Total IP Dose Administration – IV Double-blind (Unblinded)” eCRF page.

In addition:

- Randomized patients for whom it is unclear whether they took the study drug will be included in the safety population as randomized.
- For randomized patients receiving both evinacumab and placebo study treatment during the trial, the treatment group allocation for as-treated analysis will be evinacumab.
- If a randomized patient receives both evinacumab doses (300 mg SC and 450 mg SC for Group A; 5 mg/kg IV and 15 mg/kg IV for Group B), the treatment group allocation for as-treated analysis will be the most frequently administered evinacumab dose.

